9. RISKS AND BENEFITS OF THE INVESTIGATIONAL DEVICE AND CLINICAL INVESTIGATION

9.1. Potential Risks Related to Participating in this Clinical Investigation

Potential Risks of General Anesthesia

The Acoustic Enhancer with URS-LL procedure and URS-LL are performed under general anesthesia and are associated with potential anesthesia risks:

- Adverse reaction to anesthesia
- Bleeding at anesthesia instrumentation sites
- As with any procedure performed with sedation or anesthesia, there is risk associated that includes heart attack, stroke, and even death.

Potential Risks of the Acoustic Enhancer with Laser Lithotripsy Procedure

The potential risks associated with the Acoustic Enhancer with URS-LL procedure are expected to be similar to those of traditional URS-LL procedures used to treat urinary stones, with the addition of the risks for Acoustic Enhancer described in "Acoustic Enhancer Risks" described below. Potential risks for ureteroscopic laser lithotripsy generally are:

- Common (greater than 10% of subjects)
 - Mild burning sensation or hematuria for a short period after operation
 - Need for temporary insertion of a bladder catheter
 - Need for insertion of ureteric stent with a further procedure to remove it
 - As with other treatments for urinary stones, sloughed tissue found in or on urinary stones may be released as a result of a URS-LL treatment.
- Occasional (2% to 10% of subjects)
 - Kidney injury or infection needing further treatment
 - Failure to pass the ureteroscope if the ureter is narrow
- Rare (less than 2% of subjects)
 - Damage to the ureter with need for open surgical intervention or nephrostomy tube placement
- Scarring or stricture with persistent hydronephrosis/hydroureter requiring intervention

For the purposes of this protocol:

- Acute ureteral obstruction is defined by the presence of severe pain, persistent severe nausea or vomiting with per os intolerance requiring hospital admission with treatment requiring intravenous analgesics, or insertion of a ureteral stent or nephrostomy tube. Evidence of stone fragments in the ureter in diagnostic images is not sufficient for a diagnosis of urinary tract obstruction.
- Chronic ureteral obstruction is defined as persistent hydronephrosis identified on two sequential imaging studies from the same subject performed 4-6 weeks apart.

Potential Risks of the Acoustic Enhancer Material

The potential risks associated with the Acoustic Enhancer in the urinary tract during the investigational study procedure are:

Remote risks (≤ .01% of subjects)

 Acoustic Enhancer may cause an allergic reaction, which may range from minor itching or rash to major reaction such as anaphylactic reaction that could result in hospitalization or death. Excessive intraluminal pressure created by injection, causing backflow of urine and urinary tract rupture or urinoma formation

There is a potential risk associated with Acoustic Enhancer of an allergic reaction (less than 1 in a 10,000 subjects) or anaphylactic reaction (less than 1 in 20,000 subjects).

The placement of the Acoustic Enhancer closely resembles the manner in which irrigation fluid is delivered into the upper urinary tract in standard URS-LL. As such, there is a very low risk of adverse events associated with the increased pressures in the urinary tract arising during Acoustic Enhancer placement. Differential pressure risks include the pressure from backflow of urine in the urinary tract system, and in rare cases rupture in the urinary tract or urinoma formation.

As with any procedures in which ureteroscopes and other instruments are inserted into the urinary tract and materials placed using a cystoscope (narrow tube) into the urinary tract, in very rare cases, portions of the urinary tract could become inflamed or infected. While it is common practice to push a ureteral stone into the kidney prior to laser lithotripsy, there is also the potential risk of inadvertently doing so and of ureteral perforation from passage of the ureteroscope or other aspects of ureteroscope usage.

Significant new findings that may affect the subject's safety or willingness to continue in the study will be communicated to the study doctors and study subjects. An updated informed consent may be administered if appropriate.

9.2. Potential Benefits

URS-LL is routinely performed to treat urinary stones. This use of Acoustic Enhancer in URS-LL has the potential benefit of reducing the residual fragment burden. Residual fragments following URS-LL are associated with post-operative morbidity, potential readmission, and longer-term sequelae, thus reducing residual fragments in URS-LL is increasingly prioritized in the endourology community. [8] [9].

Placing Acoustic Enhancer through the working channel of the ureteroscope prior to administration of laser energy and at additional intervals during the procedure also has the potential benefit of shortening the required lasering time, with associated benefits of reduced heat generation and shortened time under general anesthesia during URS-LL procedures.

CONFIDENTIAL Page 31 of 53

9.3. Mitigation of Risks

Risk to study subjects are mitigated in this study by the following:

- All investigations are conducted by investigators who are qualified by training and experience in the treatment of patients with urinary stones.
- All assessments are procedures performed in the controlled context of a clinical trial.
- Monitoring of the clinical trial to ensure compliance and with a focus on potential safety issues.
- All investigators will be trained to the Acoustic Enhancer IFU.

10. STATISTICAL METHODS

10.1. General Considerations

The study results will be reported using descriptive summaries and data will be made available in listings or electronic format as required. The data will be summarized according to randomized treatment group (investigational arm and control arm). Inferential analyses will be performed for the primary endpoints and other endpoints as outlined below. For continuous variables, descriptive statistics will include means, standard deviations, medians and ranges. Categorical variables will be summarized in frequency distributions and reported with the count and percentages. Percentages will be calculated based on observed values. Except for the primary effectiveness endpoint analyses, a two-sided p-value less than or equal 0.05 will be considered statistically significant. The primary effectiveness analyses p-values associated with statistical significance are outlined below. Where reported, all confidence intervals will be two-sided 95% CIs.

A separate Statistical Analysis Plan will be constructed with additional detail on statistical considerations and content of tables, listing and figures from the various data analyses. Statistical analyses will be performed using SAS (version 9.4 or higher, SAS Institute Inc. Cary, NC), R (version 3.0 or higher, R Foundation for Statistical Computing, Vienna, Austria) or other widely accepted statistical or graphical software.

Results will additionally be stratified according to stone location (the upper (superior) pole, lower (inferior) pole, and interpolar region of the kidney, pelvis of the kidney, and proximal ureter) and stone diameter (< median, > median where the median is based on all ITT subjects).

10.2. Analysis Population

The study results will be summarized based on three populations:

Intent-to-Treat (ITT): The ITT population consists of all randomized subjects who meet the study inclusion/exclusion criteria. Subjects who develop UTI or having their stone move to the middle/distal ureter between the time they were screened and were found to be eligible at the time they were randomized, or who no longer meet any of the other inclusion/exclusion criteria at the time of the procedure, will not be treated under the protocol. These subjects will not be included in the ITT analysis. The ITT population will be used for all effectiveness analyses with groups based on the randomized treatment.

Safety Population: The Safety population consists of all subjects who had a procedure performed. The Safety population will be used for the safety summaries (adverse events or strictures) with groups based on the actual treatment received.

CONFIDENTIAL Page 32 of 53

Acoustic Enhancer Research on Laser Lithotripsy (AEROLITH) Clinical Study

Per-Protocol Population (PP): The Per-Protocol population will consist of all subjects who complete the primary endpoint information without a major protocol deviation; PP will include subjects who have evaluable CTs both at baseline and at 30-day follow-up. The PP population analyses will be completed based on the randomized treatment arm.

The definition of major protocol deviations will be defined prior to any final analysis. Subjects who are screened but not randomized will not be included in analysis. Any information on these subjects will be made available in a listing if requested by the IRB or FDA.

10.3. Sample Size Justification

A sample size of 196 enrolled and randomized subjects randomized 1:1 to the investigational arm (Acoustic Enhancer with URS-LL) and the control arm (URS-LL) was selected based on consideration of the primary endpoint. Assuming no more than 10% non-evaluable subjects, this provides a randomized sample size 176 subjects (88 per arm).

The primary hypothesis test for the treatment success outcome is as follows:

```
H_0: p_{AE} \le p_{Control} vs H_1: p_{AE} > p_{Control}
```

Where p_{AE} is the acoustic enhanced response rate and $p_{Control}$ is the control response rate (no acoustic enhancement). Using a one-sided 0.025 Farrington-Manning test, a 55% response rate in the control arm, and a 75% response rate in the investigational arm, the sample size provides 80% power for the analysis. The 55% control arm response rate is based on reported results for laser lithotripsy with CT- based follow-up as described in section 1.1, while the 75% response rate in the investigational arm is based on exploratory clinical studies.

10.4. Handling of Missing Data

The primary analysis of effectiveness will be based on data multiple imputation (MI) approach using the ITT Population. For the primary effectiveness endpoint, the observed results and a tipping point sensitivity analysis will also be completed as outlined in Section 10.6. No imputation or adjustment for missing data will be used for the other endpoints.

10.5. Adjustments for Multiplicity

The study will include a single primary effectiveness endpoint to be tested at the one-sided 0.025 level. If that hypothesis is met, two other endpoints will be considered sequentially. If the first secondary hypothesis is statistically significant, the second hypothesis will also be assessed. Hence, the overall Type I error for the study is controlled for the specified hypotheses.

Secondary Hypothesis 1:

Evaluation of non-inferiority of the normalized total radiant energy (TRE) will be evaluated based on the difference in the means of the log transformed values of the TRE for the investigational and control subjects, respectively. Normalized TRE is the total procedure radiant energy divided by the stop area. A non-inferiority bound of 0.223 will be considered evidence of non-inferiority (see Section 10.7 for discussion of non-inferiority bound). The hypothesis is as follows:

H₀: $\mu_{AE} \ge \mu_{Control} + \delta$ vs H₁: $\mu_{AE} < \mu_{Control} + \delta$

CONFIDENTIAL Page 33 of 53 Where μ_{AE} is the mean of the log of the total radiant energy values for the Acoustic Enhancer, $\mu_{Control}$ is the mean of the log of the total radiant energy values for the Control group, and δ is the non-inferiority bound (δ = 0.223). This will be analyzed using a one- sided 0.025 T-test.

The geometric means for each group will also be displayed by showing the exponentiation of the mean of the log transformed values. Similarly the geometric mean ratio (GMR) and associated 95% CI will be provided by showing the exponentiation of the difference means of the log values and the associated 95% CI values.

Secondary Hypothesis 2:

Reduction in normalized TRE will be analyzed by considering difference in the means log of normalized TRE. The hypothesis is as follows:

 $H_0: \ \mu_{AE} \geq \mu_{Control} \ vs \ H_1: \ \mu_{AE} < \mu_{Control}$

Where μ_{AE} is the mean of the log of the total radiant energy values for the Acoustic Enhancer and $\mu_{Control}$ is the mean of the log of the total radiant energy values for the Control group. This will be analyzed using a one- sided 0.025 test.

10.6. Primary Endpoint Analysis

The primary endpoint is defined as:

Treatment success: Proportion of study subjects who have a complete absence of stone(s), or have any residual fragments measuring less than or equal to 2 mm, as assessed by CT imaging through 30 days follow-up post index procedure. CT imaging will be assessed by an independent core lab to determine treatment success. Treatment success, as defined by an absence of residual fragments >2mm on any dimension, has been identified as a priority in stone care in recent publications including Margaret Pearle's widely cited "Is Ureteroscopy as Good as We Think", published in the Journal of Urology in 2016 [12]. Increasing awareness and clinical prioritization of residual fragments in ureteroscopic laser lithotripsy derives in large part from expanded use of CT follow-up imaging in stone subjects. CT imaging has allowed characterization of rates of residual fragments and full appreciation of their clinical significance, with rigorous studies of residual fragment natural history having established a 2mm threshold as a critical size above which additional stone events are particularly frequent [22], [23]. Therefore, a demonstration of a lower rate of >2mm residual fragments in the Acoustic Enhancer arm compared to the control arm would be clinically important.

Treatment success will be summarized descriptively as a categorical variable by treatment group. Exact binomial 95% CIs for success rates within each group will be provided

The primary analysis is to be completed on the ITT population for the hypothesis identified in Section 10.3 (H0: pAE \leq pControl vs H1: pAE > pControl). In order to account for possible missing data, the primary analysis will be completed using a multiple imputation (MI) approach and estimates of treatment differences and standard errors for the differences obtained for each MI sample using Farrington-Manning estimates. The MI model for response will be fit using a logistic approach by treatment group and include stone size, and number of stones. The estimated variance for the difference in groups will be based on combining the average variance from the imputed samples and the variance

CONFIDENTIAL Page 34 of 53 between the samples. The analysis may be completed using SAS MI and MIANALYZE procedures or through the R MICE package. The primary analysis results will include the two-sided 95% CI the difference and the one-sided p-value for the hypothesis test.

In addition, the Farrington-Manning test will be used to complete the analysis using the observed data. The two-sided 95% CI for the difference in observed data rates will be provided as well as the p-value. Note that all Farrington-Manning tests variances will be based on the sample variance under the null assumption the null groups results are equal. A tipping point analysis will be provided for evaluating the impact of missing data by imputing at the possible distribution of unavailable responses in the ITT populations. The treatment success analysis will also be completed in the per- protocol population.

The homogeneity of the treatment response will be evaluated using the available data and a logistic model of treatment success as a function of treatment, study site, and a site-treatment interaction. A p-value of less than or equal to 0.15 in the site-treatment term will be considered evidence of heterogeneity of the treatment effect across sites. In addition, as an exploratory analysis, a logistic model will be used to if stone location is associated with response or a location-treatment interaction.

10.7. Secondary Endpoint Analysis

The secondary endpoint is defined as:

Total radiant energy (TRE): Mean value of laser energy, measured in kilojoules, with laser energy values recorded and displayed by the pulsed laser unit used in the procedure, with the laser energy value for each procedure normalized by the stone cross-sectional area. For this purpose, the stone cross-sectional area is calculated by taking the product of the two largest stone size measurements on the preprocedure CT; for subjects with more than one stone treated in the index procedure, the stone cross-sectional area is calculated as the sum of the stone cross-sectional areas calculated individually for each treated stone. The mean value of laser energy for each arm is calculated by considering the normalized measured values for all study subjects in that arm.

Normalized TRE will be summarized as a numeric variable. In addition, as the primary analysis is based on ratio of the means, the geometric mean and 95% CIs based on the back-transformation of the log values will be provided. The log-transformed values will also be summarized descriptively. All analyses of TRE will be based on available data. TRE is to be collected as part of the procedure and it few if any missing values are expected. If more than 4 subjects have missing TRE values, a MI analysis will be completed as a sensitivity analysis.

In support of the secondary hypotheses (Section 10.5), a t-test will be used to assess the difference in between groups in the means of the log-transformed normalized TRE value. If the two-sided 95% CI upper bound of the difference in the means is less than 0.223 (log 1.25) then secondary hypothesis 1 will be considered met and if bound is less than -0.0, the secondary hypothesis 2 will also be considered met. The one-sided p-values associated with the hypothesis will also be provided.

The ratio cut-off of 1.25 for the non-inferiority assessment was obtained based of review of papers describing total energy (Molina et al (2014), Humphreys et al (2018), and Rana, et al (2020)). Further, discussion with investigators indicated the endpoint could have considerable variability based on uniqueness of the individual subject, stone size, stone composition, and stone location. The Molina (2014) paper included analyses of total energy and found several significant predictors but at best the explained about half the variance (R2 = 0.524 for a multivariate model). Molina (2014) presented an exploration of total energy normalized by stone volume.

CONFIDENTIAL Page 35 of 53

Acoustic Enhancer Research on Laser Lithotripsy (AEROLITH) Clinical Study

Based on normalized TRE from the paper it appears as the ratio of the upper quartile to the median was approximately 1.6. The ratio of 1.25 would reflect a ratio of AE to control that would be close the control mean and well within variability associated with a single standard deviation. Hence, given the inherent variability of the measure, the use of 1.25 as a ratio to indicate non-inferiority normalized TRE is justified.

The Wilcoxon Rank-Sum test will be used as a confirmatory analysis of the t-test for a comparison of the observed normalized TRE. If more than 4 subjects have missing TRE values, a multiple-imputation analysis will be performed including group and the total stone area as predictive covariates. The homogeneity of the treatment response will be evaluated using a ANOVA model of normalized total radiant power as a function of treatment, study site, and a site-treatment interaction. A p-value of less than or equal to 0.15 in the site-treatment term will be considered evidence of heterogeneity of the treatment effect across sites. In addition, as an exploratory analysis, an ANOVA model will be used if stone location is associated with response or a location-treatment interaction.

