5.7. Inclusion Criteria

- 5.7.1. Male or female aged \geq 18 years to \leq 75 years
- 5.7.2. Provides written informed consent
- 5.7.3. Patients with at least one urinary stone measuring 6mm or greater (but no more than a cumulative diameter of 20mm) located proximally to the iliac vessels on one side may be treated.

Note 1: Punctate stones measuring $\leq 2mm$ do not count in the cumulative diameter limit. **Note 2:** Some corroborating imaging may be required to exclude a patient if the investigator suspects that the stone has moved to middle/distal ureter (e.g. change in symptoms, an increase in serum creatinine).

5.7.4. Urinary stone(s) should be apparent on a CT scan within 60 days prior to study enrollment.
 Stone assessment will be conducted using CT imaging following CLIN-0025:
 AEROLITH IDE Study Screening Guide

Note 1: Soft tissue window will be used for stone measurement. Window width/level adjustments will be applied as necessary by the reviewer to improve stone evaluation. A bone window may help distinguish stones from ureteral stents. The region of interest will be magnified (approximately 400%) by the reviewer to clearly visualize the stone outline. For details, please refer to CLIN-0003. **Note 2:** If CT imaging has not been conducted yet for the patient, please follow CT image acquisition parameters detailed in CLIN-0002: Image Acquisition Protocol, AEROLITH Study

- 5.7.5. Patients with bilateral stones are allowed but only one side may be treated. Only the treated side will be evaluated for safety and effectiveness.
- 5.7.6. Patient may enter the study with a stent in place.

5.7.7. Patients presenting with absence of a Urinary Tract Infection as confirmed using urinalysis

Note: If the urinalysis is more than 7 days removed on the day of the procedure, a urinalysis and confirmation that the patient is free of UTI symptoms should be performed on the day of the procedure for the patient to be eligible to participate in the study.

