8. SUBJECT ASSESSMENT AND STUDY VISIT SCHEDULE AND PROCEDURES

8.1. Pre-Treatment Visit

After the subject has completed the informed consent process, research staff will review potential subject's medical history, including available images, to verify study subject's eligibility. In addition, research staff will conduct protocol required assessments prior to the index procedure to obtain baseline information and verify subject eligibility.

- As part of routine care, study subjects may be prescribed medications such as analgesics, alpha blockers, calcium channel blockers, antibiotics to take as needed.
- Research staff will review subject's medical history, including available images, to verify study eligibility.
- Subjects will complete a baseline health status and undergo focused urogenital calculus physical exam and vital signs.

- Subjects will undergo a CT scan to measure stone dimensions (in mm), and location (e.g., the upper (superior) pole, lower (inferior) pole, and interpolar region of the kidney, pelvis of the kidney, and proximal ureter). This will be noted on the Electronic Case Report Form (eCRF). If there are multiple stones, each one will need to be measured and its location (i.e., pelvis, ureter), size will be documented.
 - CT image acquisition parameters will follow CLIN-0002: Image Acquisition Protocol, AEROLITH Study. A CT image collected prior to screening may be used as baseline CT image. The CT image will be used to measure stone size and the location of the stone.
 - Measuring baseline stone size(s) will be conducted by the investigator following CLIN- 0003: Radiographic Evaluation Protocol of Applaud's Acoustic Enhancer with Laser Lithotripsy System in the Treatment of Urinary Stones
 - A Stone Size Measurement Verification Electronic Case Report Form (eCRF) will be completed by the investigational site and the baseline CT image will be uploaded to the core lab for analysis following CLIN-0003.
- Subjects will undergo a urinalysis to verify absence of Urinary Tract Infection (UTI) and verify pH level is ≥ 5.5. *Note:* If a patient's largest stone intensity is ≥ 500HU and has a historical pH value of ≥ 5.5, a recently tested (within 30 days of consent) urine pH showing <5.5 in this case is acceptable.
- Serum creatinine to verify renal function and serum creatinine is < 1.5mg/dl.

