6.4.2 Baseline Disease Status/Disease History

Disease history information will be collected on the Urinary Stone History form, which include:

- History of treatment procedures in study/treatment side (Yes/No)
- Existence of stent in place and whether the stent appears calcified or encrusted is in place
- Existence of radiolucent stones on KUB or Scout CT Imaging and the imaging modality used to access radiolucent stones if radiolucent stones are present

Disease status information will be collected on the Vital Signs/Physical Exam form and the Stone Location and Measurement form, which includes:

- Conduct of focused urogenital calculus physical exam and abnormality if conducted (Abnormal findings/No abnormal findings)
- Location of each stone (investigator reported)
- Largest diameter (mm) of each stone (investigator reported)
- Cumulative diameter (mm) of all stones (investigator reported)

Urinary stone history and stone location and measurement will be presented in separate bysubject listings and summarized together overall and by treatment group using the ITT, PP and Safety populations.

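### Optional efficiency gain: the primary comparison is valid but leaves out baseline stone size and number of stones, which the plan already uses to impute the same outcome

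*Protocol*

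**What the plan says.** Protocol 10.6 runs the primary analysis on multiply imputed data, with "estimates of treatment differences and standard errors for the differences obtained for each MI sample using Farrington-Manning estimates". No covariate enters that comparison, and "all Farrington-Manning tests variances will be based on the sample variance under the null assumption". The preceding step does use covariates: "The MI model for response will be fit using a logistic approach by treatment group and include stone size, and number of stones".

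The remaining models for treatment success in 10.6 are "a logistic model of treatment success as a function of treatment, study site, and a site-treatment interaction" and an exploratory model with stone location. Protocol 10.1 also presents results by stone location and by stone diameter split at the median, which gives strata but no adjusted comparison of the arms.

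Both covariates are known before treatment. Under Protocol 8.1, every stone is measured on the pre-treatment CT, and "Measuring baseline stone size(s) will be conducted by the investigator". SAP 6.4.2 lists the largest diameter of each stone and the cumulative diameter, both as read by the investigator.

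The Synopsis and Protocol 6.6 define study success by the Farrington-Manning p-value. SAP 5.1 plans no covariate adjustment, but SAP 5 and 8.1.1 send the primary analysis to a separate plan that is not among the documents.

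**The concern.** The plan treats stone size and number of stones as useful predictors of success, yet it uses them only for the roughly 10% of outcomes expected to be missing. If they predict success, part of the outcome variance in every arm could be removed with data the trial already collects. Standardizing a logistic model over values fixed before randomization estimates the same marginal risk difference, so the hypothesis in Protocol 10.3 would not change.

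What is at stake is precision. Study success rests on this one test, and it has 80% power at the planned maximum loss. Chance imbalance in stone burden is already covered by the unadjusted standard error, so bias is not at issue.

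**Working it through.** **1. The plan's own figure.** Inputs from Protocol 10.3: 55% vs 75%, one-sided 0.025, 88 evaluable per arm. At zero margin, Farrington-Manning uses the pooled null variance:

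power = Φ{[0.20 − 1.96·√(2·0.65·0.35/88)] / √[(0.55·0.45 + 0.75·0.25)/88]} = Φ{(0.20 − 0.1409)/0.0703} = Φ(0.840) = 79.96%.

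Exact enumeration gives 80.3%. 176/0.9 rounds up to 196. The stated 80% reproduces.

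**2. Validity without covariates.** The exact one-sided type I error of the unadjusted test is 2.5–2.8% at 88 per arm and 2.4–2.6% at 98 per arm, for common success rates of 45–65%. That is close to nominal.

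**3. Gain by formula.** The documents give no figure for how strongly stone burden predicts success. Let R² be the assumed share of outcome variance explained, and multiply both variances in step 1 by (1 − R²):

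| R² | 0 | 1% | 3% | 5% | 10% | 15% |
|---|---|---|---|---|---|---|
| Power | 80.0% | 80.4% | 81.2% | 82.0% | 84.0% | 86.0% |

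For scale, suppose success differs by 20 points between the lower and upper halves of stone burden, as much as the assumed treatment effect. The variance sum 0.435 falls by 2·(0.10)² to 0.415, so R² = 4.6% and power is 81.8% (+1.8 points).

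**4. Gain by simulation, type I error held equal.** Assumptions: cumulative diameter uniform over 6–20 mm (the entry limits in Protocol 5.7; SD 14/√12 = 4.04 mm), a log-odds slope per SD, and number of stones correlated with diameter but without an effect of its own. The adjusted estimate is a standardized logistic risk difference with an influence-function variance and small-sample correction. Its critical value was set so that its null rejection rate equals that of Farrington-Manning (FM). The complete-data columns use 88 per arm and show the lowest adjusted power over three null rates. The imputed columns use 98 per arm, with missingness depending on burden. Gains come from unrounded figures.

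| Slope per SD | Control success, 6 vs 20 mm | Complete data: FM, adjusted (gain) | Imputed data: FM, adjusted (gain) |
|---|---|---|---|
| 0 | 55% vs 55% | 80.3, 80.0 (−0.3) | not run |
| 0.2 | 63% vs 46% | 80.4, 80.2 (−0.2) | 80.5, 80.7 (+0.2) |
| 0.4 | 71% vs 38% | 80.5, 81.3 (+0.9) | 79.2, 80.0 (+0.7) |
| 0.5 | 75% vs 34% | 80.5, 82.0 (+1.5) | 79.8, 81.7 (+1.9) |
| 0.8 | 83% vs 24% | 80.4, 84.8 (+4.5) | 80.3, 84.0 (+3.6) |
| 1.0 | 88% vs 18.5% | 80.6, 86.9 (+6.4) | 79.9, 85.1 (+5.2) |

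Before equalizing, type I error was 2.4–2.9% for FM and 2.5–2.9% for the adjusted test. Without equalizing, about 0.5 point of each apparent gain comes from the unpooled variance and not from the covariates.

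**5. A narrower range of stones.** If diameters lie within 6–12 mm, the SD is 6/√12 = 1.73 mm. The same slopes per mm then become 1.73/4.04 = 0.43 times as large per SD, so the steepest case (1.0) becomes 0.43 and gains only about 1–1.5 points.

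**6. What a point is worth.** The step 1 formula needs 90.4 per arm for 81% power and 92.7 for 82%. A gain of 1–2 points therefore equals about 2–5 more evaluable subjects per arm. FM power is 82.2% at 5% loss and 84.1% at no loss.

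**The case against.** The case for leaving the plan alone is substantial.

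- **No defect.** The unadjusted test matches the hypothesis, the sample size and the success rule. Using covariates to impute does not oblige a plan to use them in the comparison. This stands.
- **The benefit is assumed.** A gain of about 4 points or more needs the steep gradients in the last two rows of step 4. Protocol 8.2 has lasering continue until visible fragments reach a fixed small size whatever the starting burden, and the entry limits restrict the range. Either could flatten the gradient. This stands.
- **Retention could do as much.** The 10% loss is a planned maximum, and 5% loss alone would give 82.2%. This stands.
- **Replacing the test is costly.** The revision history says the success rule was added to address an FDA study consideration. This weighs against changing the primary test, but not against a supportive analysis.
- **The proposed model is incomplete.** It omits site, on which randomization is blocked, and step 4 gives number of stones no effect of its own. The planned test omits site too. A separate simulation in which size and number both carried effects, with imputation, gave +0.7, +1.0 and +2.1 points at R² of 1.0%, 2.5% and 4.7% (type I error not equalized; Monte Carlo error up to about 1 point), which is a similar size.

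Some stronger readings are tempting but unsupported. A reader might infer that the primary test is biased or invalid; steps 1 and 2 show otherwise. A reader might take SAP 5.1 as ruling out adjustment of the primary analysis, but that SAP does not cover it. The R² of 0.524 in Protocol 10.7 concerns laser energy, not treatment success. The remark in Protocol 1.2 on stones above 6 mm justifies the entry threshold and says nothing about the gradient among eligible subjects.

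**Conclusion.** The point holds as an optional, low-severity improvement in efficiency. The protocol's text compares the arms without two baseline variables that it uses to predict the same outcome, and the diameter strata do not fill that gap.

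With type I error held equal, the change in power is about −0.3 to +2 points for a slope of 0–0.5 log-odds per SD (up to about 5% of outcome variance explained). It is about 4–6 points only for a slope of 0.8–1.0. These sizes rest wholly on the assumed prognostic strength and on the assumed 6–20 mm spread. The conclusion concerns the protocol's wording, because the separate efficacy plan may already adjust. The finding of validity covers only the omission of covariates, not other features of the analysis.

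**What to change.** First check the separate efficacy plan. If it does not adjust, then before any comparison of outcomes by arm:

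1. Pre-specify in Protocol 10.6 and in that plan a logistic model of success on treatment, screening cumulative stone diameter (investigator reading) and number of stones, fitted in each imputed data set. Standardize it to the marginal risk difference, use a robust variance with a small-sample correction, and pool by Rubin's rules.
2. Name the same diameter measure in the imputation model, where 10.6 says only stone size. This is worth doing even if nothing else changes.
3. Make the adjusted estimate the primary test, at one-sided 0.025, only if the regulator agrees and the success rule (Synopsis, Protocol 6.6) and Protocol 10.3 are amended to match, with Farrington-Manning kept as supportive. Otherwise leave the named test and success rule unchanged and report the adjusted estimate as the first supportive analysis.

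Cost: no new data and little programming. Replacing the test puts up to about 0.3 power point at risk if burden is not prognostic, brings in a less familiar estimator and needs a protocol amendment. The supportive version needs only pre-specified text.
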